2.8.2 Deaths

Separate summaries for on-treatment deaths will be produced by treatment arm, SOC and PT.

All deaths will be listed for the Safety set and post-treatment deaths will be flagged. A separate listing of deaths prior to starting treatment will be provided for all screened subjects, if any.

2.8.3 EudraCT and clinicaltrials.gov requirements for AEs and Deaths summaries

For the legal requirements of clinicaltrials.gov and EudraCT, two required tables on on-treatment/treatment-emergent AEs which are not serious AEs with an incidence greater than 5% and on on-treatment/treatment-emergent SAEs and SAEs suspected to be related to study treatment will be provided by SOC and PT on the Safety set population.

If for a same subject, several consecutive AEs (irrespective of study treatment causality, seriousness and severity) occurred with the same SOC and PT:

- A single occurrence will be counted if there is ≤ 1 day gap between the end date of the preceding AE and the start date of the consecutive AE
- More than one occurrence will be counted if there is > 1 day gap between the end date of the preceding AE and the start date of the consecutive AE.

For occurrence, the presence of at least one SAE / SAE suspected to be related to study treatment / non SAE has to be checked in a block, e.g., among AEs in a ≤ 1 day gap block, if at least one SAE is occurring, then one occurrence is calculated for that SAE.

The number of deaths resulting from SAEs suspected to be related to study treatment and SAEs irrespective of study treatment relationship will be provided by SOC and PT.

2.8.4 Adverse events of special interest / grouping of AEs

An AESI is a grouping of AEs that are of scientific and medical concern specific to compound INC280. These groupings are defined using MedDRA terms, SMQs (standardized MedDRA queries), HLGs (high level group terms), HLTs (high level terms) and PTs (preferred terms).

Customized SMQs (Novartis MedDRA queries, NMQ) may also be used. A NMQ is a customized group of search terms which defines a medical concept for which there is no official SMQ available or the available SMQ does not completely fit the need. It may include a combination of single terms and/or an existing SMQ, narrow or broad. Pre-defined AESIs for the current study are as follows:

- Hepatotoxicity
- Central nervous system (CNS) toxicity
- Interstitial Lung Disease and Pneumonitis
- QTc interval prolongation
- Pancreatitis
- Drug-drug interactions with strong CYP3A4 inducers
- Teratogenicity
- Renal dysfunction
- Photosensitivity

For each specified AESI, number and percentage of subjects with at least one event of the AESI occurring during on-treatment period will be summarized.

Summaries of these AESIs will be provided by treatment arm (INC280 + PEMBRO and PEMBRO alone). A listing of all grouping levels down to the MedDRA PTs used to define each AESI will be generated.

Note: From the eCRS, only risk where “Core Safety Risk” = Y should be selected to report AESI in the CSR (the variable name in GPS, for “Core Safety Risk”, is “SP”).

2.8.5 Laboratory data

2.8.5.1 CTC grading for laboratory parameters

Grade categorization of lab values will be assigned programmatically as per NCI CTCAE version 5.0. The calculation of laboratory CTC grades will be based on the observed laboratory values only; clinical assessments will not be taken into account. The criteria to assign CTC grades are given in Novartis internal criteria for CTC grading of laboratory parameters. The latest available version of the document based on the underlying CTCAE version 5.0 at the time of analysis will be used.

For laboratory tests where grades are not defined by CTCAE version 5.0, results will be graded by the low/normal/high (or other project-specific ranges, if more suitable) classifications based on laboratory normal ranges.

A severity grade of 0 will be assigned for all non-missing lab values not graded as 1 or higher. Grade 5 is not applicable. For laboratory tests that are graded for both low and high values, summaries will be done separately and labeled by direction, e.g., sodium will be summarized as hyponatremia and hypernatremia.

2.8.5.2 Data analysis

The summaries will include all assessments available for the lab parameter collected no later than 30 days after the last study treatment administration date (see [Section 2.1.1.5](#)).

The following summaries will be produced for hematology and biochemistry laboratory data (by laboratory parameter and treatment):

- Worst post-baseline CTC grade (regardless of the baseline status). Each will be counted only for the worst grade observed post-baseline;
- Shift tables using CTC grades to compare baseline to the worst on-treatment value;
- For laboratory tests where CTC grades are not defined, shift tables using the low/normal/high/(low and high) classification to compare baseline to the worst on-treatment value.

The following listings will be produced for the laboratory data:

- Listing of all CTC grade 3 or 4 laboratory toxicities.

Liver function parameters

Liver function parameters of interest are TBIL, ALT, AST and ALP.

The number (%) of subjects with worst post-baseline values will be summarized:

- ALT or AST > 3×ULN
- ALT or AST > 5×ULN
- ALT or AST > 8×ULN
- ALT or AST > 10×ULN
- ALT or AST > 20×ULN
- TBIL > 2×ULN
- TBIL > 3×ULN
- ALT or AST > 3×ULN & TBIL > 2×ULN
- ALT or AST > 3×ULN & TBIL > 2×ULN & ALP < 2×ULN (potential Hy's law).

Potential Hy's Law events are defined as those subjects with concurrent occurrence of AST or ALT > 3×ULN and TBIL > 2×ULN and ALP < 2×ULN in the same assessment sample during the on-treatment period. Further medical review has to be conducted to assess potential confounding factor such as liver metastases, liver function at baseline, etc.

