6.5.1 Dose modifications

For subjects who do not tolerate the protocol-specified dosing schedule, dose interruptions and/or reductions are either recommended or mandated in order to allow subjects to continue the study treatment.

In situations where the causality of toxicity cannot be clearly attributed to one of the study drugs (capmatinib or pembrolizumab), dose modification recommendations for both study drugs should be followed.

There are no dose reductions allowed in this study for pembrolizumab. Dose interruptions for pembrolizumab are permitted. Please refer to local pembrolizumab labels for recommended treatment modifications for pembrolizumab.

For clinical management of suspected immune-related adverse event (irAE) and corresponding dose modification requirements, reference to consensus management guidelines is recommended such as those provided in the National Comprehensive Cancer Network (NCCN) Guidelines for the Management of Immunotherapy-Related Toxicities (available at:

https://www.nccn.org/professionals/physician_gls/default.aspx#immunotherapy), the American Society for Clinical Oncology (ASCO) clinical practice guideline for Management of Immune-Related Adverse Events in Subjects Treated With Immune Checkpoint Inhibitor Therapy (Brahmer et al 2018) or the European Society for Medical Oncology (ESMO) Clinical Practice Guidelines for Management of Toxicities from Immunotherapy (Haanen et al 2017).

Consider early referral to specialists with expertise in the diagnosis and management of immune-related AEs to thoroughly investigate events of uncertain etiology.

Events not included in the study protocol or the reference guidance documents should be managed per institutional preference.

Dose reductions and interruptions are permitted for capmatinib. These dose modifications are summarized in Table 6-6. Deviations to mandatory dose interruptions and/or reductions are not allowed. Permanent treatment discontinuation for capmatinib is mandatory for specific events indicated as such in Table 6-6.

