6.5.2 Follow-up for toxicities

Following approval of protocol amendment 03, please refer to the locally approved pembrolizumab label and follow each institution’s standard of care to ensure adequate monitoring and follow-up of toxicities. The content of Section 6.5.2 below and Table 6-7 are no longer applicable.

Subjects whose treatment is interrupted or permanently discontinued due to an adverse event or clinically significant laboratory value, must be followed up at least once a week (or more frequently if required by institutional practices, or if clinically indicated) for four weeks, and subsequently at approximately four week intervals, until resolution or stabilization of the event, whichever comes first. Appropriate clinical experts such as ophthalmologists, endocrinologists, dermatologists, psychiatrists etc. should be consulted as deemed necessary. All subjects must be followed for AEs and SAEs after discontinuation of pembrolizumab and capmatinib. Recommendations for follow-up evaluations of selected toxicities for subjects receiving capmatinib refer to Table 6-7.

The emergence of irAE may be anticipated based on the mechanism of action of immunomodulatory therapies. Serologic, histologic (tumor sample) and immunological assessments should be performed as deemed appropriate by the investigator locally to verify the immune-related nature of the AE and to exclude alternative explanations.

Subjects whose treatment is temporarily interrupted or permanently discontinued due to an AE or abnormal laboratory value must be followed until resolution or stabilization of the event, whichever comes first, including all study assessments appropriate to monitor the event.

An unscheduled assessment should be performed in all cases below where toxicity monitoring is recommended more frequently than defined by the schedule of assessments. Subsequent monitoring must be performed as per the regular visit schedule.

Table 6-7 Follow-up evaluations for selected toxicities – obsolete upon approval of protocol amendment 03

TOXICITY	FOLLOW-UP EVALUATION
HEMATOLOGICAL	
Febrile neutropenia, Neutropenia ≥ CTCAE grade 3 Thrombocytopenia ≥ CTCAE grade 3 Anemia ≥ CTCAE grade 3	Test weekly (or more frequently if clinically indicated) until ≤ CTCAE grade 2. Perform physical exam for check on bruising in case of major thrombocytopenia.
RENAL	

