Serum creatinine ≥ CTCAE grade 2	Test weekly (or more frequently if clinically indicated) until ≤ CTCAE grade 1 or baseline. Subjects will be instructed to increase hydration until resolution to ≤ CTCAE grade 1 or baseline.

Final

TOXICITY	FOLLOW-UP EVALUATION
HEPATIC	
Isolated total bilirubin elevation	
Total bilirubin CTCAE Grade 1: Monitor liver function tests (LFTs) per protocol or more frequently if clinically indicated
 
Total bilirubin CTCAE Grade 2: Weekly monitoring of LFTs, or more frequently if clinically indicated, until resolved to $\leq 1.5 \times \text{ULN}$
 
Total bilirubin CTCAE Grade 3: Weekly monitoring of LFTs, or more frequently if clinically indicated, until resolved to $\leq 1.5 \times \text{ULN}$. If resolved in > 7 days, after discontinuing the subject from capmatinib permanently, the subject should be monitored weekly (including LFTs), or more frequently if clinically indicated, until total bilirubin have resolved to baseline or stabilization over 4 weeks
 
Total bilirubin CTCAE Grade 4: After discontinuing the subject from capmatinib permanently, the subject should be monitored weekly (including LFTs), or more frequently if clinically indicated, until total bilirubin has resolved to baseline or stabilization over 4 weeks

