Isolated AST/ALT elevation	
AST/ALT CTCAE Grade 2 elevation: For subjects with baseline value $\leq 3.0 \times \text{ULN}$: repeat LFTs as soon as possible, preferably within 48-72 hours from awareness of the abnormal results; if abnormal lab values are confirmed upon the repeat test, then monitor LFTs weekly, or more frequently if clinically indicated, until resolved to $\leq 3.0 \times \text{ULN}$ For subjects with baseline value $> 3.0 - 5.0 \times \text{ULN}$: monitor LFTs per protocol or more frequently if clinically indicated
 
AST/ALT CTCAE Grade 3 elevation: For AST/ALT elevation $> 5.0 - 10.0 \times \text{ULN}$:
 
 • For subjects with baseline value $\leq 3.0 \times \text{ULN}$: repeat LFTs as soon as possible, preferably within 48-72 hours from awareness of the abnormal results; monitor LFTs weekly, or more frequently if clinically indicated, until resolved to $\leq 3.0 \times \text{ULN}$ • For subjects with baseline value $> 3.0 - 5.0 \times \text{ULN}$: repeat LFTs as soon as possible, preferably within 48-72 hours from awareness of the abnormal results; if abnormal lab values are confirmed upon the repeat test, then monitor LFTs, weekly, or more frequently if clinically indicated, until resolved to $\leq 5.0 \times \text{ULN}$ 
For AST/ALT elevation $> 10.0 - 20.0 \times \text{ULN}$: Repeat LFTs as soon as possible, preferably within 48-72 hours from awareness of the abnormal results; monitor LFTs weekly, or more frequently if clinically indicated, until resolved to \leq baseline

Final

TOXICITY	FOLLOW-UP EVALUATION
	
AST/ALT CTCAE Grade 4 elevation: Repeat LFTs as soon as possible, preferably within 48-72 hours from awareness of the abnormal results; monitor LFTs weekly, or more frequently if clinically indicated, until resolved to baseline or stabilization over 4 weeks.

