
Combined AST or ALT and total bilirubin elevation
	
Combined elevations of AST or ALT and total bilirubin: After discontinuing the subject from capmatinib permanently, repeat LFTs as soon as possible, preferably within 48 hours from awareness of the abnormal results, then with weekly monitoring of LFTs, or more frequently if clinically indicated, until AST, ALT, or bilirubin have resolved to baseline or stabilization over 4 weeks. Core LFTs consist of ALT, AST, GGT (Gamma-glutamyl transferase), total bilirubin (fractionated (direct and indirect), if total bilirubin > 2.0 × ULN), and alkaline phosphatase (fractionated (quantification of isoforms), if alkaline phosphatase > 2.0 × ULN.)

METABOLIC	

Asymptomatic amylase or lipase ≥ CTCAE grade 3
	
Test weekly (or more frequently) until ≤ CTCAE grade 2. A CT scan or equivalent imaging procedure to assess the pancreas, liver, and gallbladder is recommended within 7 days of the first occurrence of any ≥ CTCAE grade 3 result, to exclude disease progression or potential other liver or pancreatic disease.

CARDIAC	

≥ CTCAE grade 3
	
Test weekly (or more frequently) until ≤ CTCAE grade 2.

QTcF ≥ 501 ms (CTCAE grade 3)
	
When QTcF ≥ 501 ms (CTCAE grade 3), perform the following:
 
Perform an analysis of serum potassium, calcium, phosphorus, and magnesium, and if below lower limit of normal, correct with supplements to within normal limits. Review concomitant medication usage for the potential to inhibit CYP3A4/5 (Table 6-3) and/or to prolong the QT-interval ().
 
Perform a repeat ECG within one hour of the first QTcF of ≥501 ms. If QTcF remains ≥ 501 ms, repeat ECG as clinically indicated, but at least once daily until the QTcF returns to < 501 ms.
 
Repeat ECGs 7 days and 14 days (and then every 21 days) after dose resumption for all subjects who had therapy interrupted due to QTcF ≥ 501 ms. If QTcF of ≥ 501 ms recurs, repeat ECGs as described above.
 
Notes: The investigator should contact the Novartis Medical Lead or designee regarding any questions that arise if a patient with QTcF prolongation should be maintained on study.

Final

TOXICITY	FOLLOW-UP EVALUATION
GASTROINTESTINAL	

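### Extra repeat tests recommended only under capmatinib can modestly inflate the combination arm's worst ALT/AST, bilirubin and creatinine values, because SAP 2.8.5.2 takes the worst of all samples

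*SAP*

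**What the plan says.** **Analysis.** SAP 2.8.5.2 states: "The summaries will include all assessments available for the lab parameter collected no later than 30 days after the last study treatment administration date". From these samples it tabulates, by treatment, the worst post-baseline CTC grade, shifts from baseline to the worst on-treatment value, and counts above liver thresholds (ALT or AST >3, >5, >8, >10 and >20×ULN; TBIL >2 and >3×ULN; combined rows). It plans no scheduled-visit version and no count of tests per subject.

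**Scheduled testing.** Protocol Table 8-2 has haematology and chemistry at screening, Day 1 of each 21-day cycle and EOT, the same in both arms.

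**Extra testing under capmatinib.** Protocol 6.5.2 says: "Recommendations for follow-up evaluations of selected toxicities for subjects receiving capmatinib refer to Table 6-7". The added tests are unscheduled samples: "An unscheduled assessment should be performed in all cases below where toxicity monitoring is recommended more frequently than defined by the schedule of assessments". Table 6-7 asks for:
- creatinine from grade 2: "Test weekly (or more frequently if clinically indicated) until ≤ CTCAE grade 1 or baseline";
- bilirubin from grade 2: weekly liver function tests;
- AST/ALT from grade 2: "repeat LFTs as soon as possible, preferably within 48-72 hours from awareness of the abnormal results", then generally weekly, depending on baseline and confirmation;
- haematology from grade 3: "Test weekly (or more frequently if clinically indicated) until ≤ CTCAE grade 2";
- amylase/lipase, with the trigger "Asymptomatic amylase or lipase ≥ CTCAE grade 3": weekly.

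**Pembrolizumab.** Protocol 6.5.1 has no such table: "Please refer to local pembrolizumab labels for recommended treatment modifications for pembrolizumab". It also cites general guidelines on immune-related events.

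**Rules shared by both arms.** Protocol 6.5.2 requires at least weekly follow-up for four weeks after an interruption or discontinuation for an AE or significant laboratory value. Protocol 6.5.2.1 asks for repeat liver tests within 48 hours in potential drug-induced liver injury. Protocol 8.4.1 lets investigators add laboratory time points.

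After approval of Amendment 03, safety assessment results are no longer captured on the eCRF (Protocol 8.4). The laboratory tables therefore rest on data from before that approval.

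**The concern.** The maximum of a series cannot fall when samples are added. If one arm is retested more often after a first abnormal value, its recorded worst value will tend to be higher even when the underlying laboratory courses are the same. The by-arm contrast then partly reflects how often subjects were tested.

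Enrollment was halted for lack of tolerability in the combination arm, so by-arm toxicity tables will be read closely. The arms are small (51 and 25 randomized). One subject is 1/51 = 2.0 percentage points in one arm and 1/25 = 4.0 in the other, so even a small detection effect can move a row visibly.

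**Working it through.** The plan gives no rate or power figure for these tables, so there is nothing to reproduce. The check has three steps.

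**1. Which rows can a triggered repeat change?** A repeat is sent only after an abnormal result, so compare each trigger with the row it might affect.
- *Haematology, amylase/lipase:* the trigger is grade ≥3. The subject already counts as grade 3-4, so repeats add 0 such subjects. They can only move grade 3 to grade 4.
- *ALT/AST:* grade 2 starts above 3×ULN. The >3×ULN row is already met at the trigger and cannot rise from ALT/AST repeats. The rows from >5×ULN (grade 3) upward can.
- *Bilirubin:* grade 2 starts above 1.5×ULN, so the >2 and >3×ULN rows can both rise.
- *Creatinine:* grade 2 is >1.5-3.0×ULN, so grade 3-4 can rise.
- *Across analytes:* a bilirubin trigger calls for liver tests that include ALT and AST. In principle, one analyte's trigger can raise another's row.

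**2. How large could the effect be per ALT episode?** Both arms were given identical true ALT courses (100,000 episodes per scenario). Control was tested every 21 days. Combination had the same tests plus a repeat at +3 days and then weekly while above 3×ULN.

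The assumptions, none of them from the documents, are:
- a log-triangular course from 0.7×ULN, with onset uniform within the cycle;
- mean length of 3, 6 or 9 weeks;
- a lognormal peak with median 3 or 5×ULN and log-SD 0.6;
- measurement CV of 0 or 15%.

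Probability of recording >5×ULN:

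| Weeks | Median peak (×ULN) | CV | Scheduled only | With repeats | Difference (points) | Ratio |
|---|---|---|---|---|---|---|
| 3 | 3 | 0 | 0.025 | 0.035 | 1.0 | 1.40 |
| 3 | 3 | 15% | 0.030 | 0.040 | 1.0 | 1.33 |
| 3 | 5 | 0 | 0.090 | 0.119 | 2.9 | 1.32 |
| 3 | 5 | 15% | 0.094 | 0.124 | 3.0 | 1.32 |
| 6 | 3 | 0 | 0.052 | 0.077 | 2.5 | 1.48 |
| 6 | 3 | 15% | 0.058 | 0.084 | 2.6 | 1.45 |
| 6 | 5 | 0 | 0.178 | 0.244 | 6.6 | 1.37 |
| 6 | 5 | 15% | 0.188 | 0.256 | 6.8 | 1.36 |
| 9 | 3 | 0 | 0.077 | 0.112 | 3.5 | 1.45 |
| 9 | 3 | 15% | 0.084 | 0.124 | 4.0 | 1.48 |
| 9 | 5 | 0 | 0.256 | 0.339 | 8.3 | 1.32 |
| 9 | 5 | 15% | 0.268 | 0.356 | 8.8 | 1.33 |

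Detection of >3×ULN was identical under both rules in all 12 scenarios, for example 0.221 and 0.221. Detection of >20×ULN rose by at most 0.4 points (0.002 to 0.006).

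A second set of assumed courses (median peak 4.5×ULN, log-SD 0.5, 3 to 12 weeks, CV 0-20%) left 25-34% of the >5×ULN maxima unrecorded under scheduled testing. That corresponds to ratios of 1/(1 − 0.25) = 1.33 to 1/(1 − 0.34) = 1.52. Other assumed courses reached about 1.7, so the working range is 1.3-1.7.

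**3. What does that mean in subjects?** Excess = share with an episode × difference per episode. With an assumed 10-30% of subjects having an episode, and the 12 scenarios above:
- low: 0.10 × 0.010 = 0.001, and 0.001 × 51 ≈ 0.1 subject;
- high: 0.30 × 0.088 = 0.026, and 0.0264 × 51 ≈ 1.3 subjects.

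If a share f of control episodes is retested in the same way, multiply by (1 − f). At f = 0.5 the high end is 1.35 × 0.5 ≈ 0.7 subject. The documents do not give f.

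**The case against.** The strongest reply is that testing is less unequal than Table 6-7 suggests. Weekly follow-up after interruption or discontinuation is mandatory in both arms, as is the 48-hour repeat in potential liver injury. Investigators may add tests in either arm, and Protocol 10.1.1 requires AEs to be followed to resolution. Table 6-7 is itself introduced as recommendations. This stands as a limit on size, but it does not restore symmetry. The 48-hour rule needs combined transaminase and bilirubin elevation, so it does not cover isolated ALT/AST. Table 6-6 also adds capmatinib-specific interruption triggers (creatinine and bilirubin grade 2, for example), which give the combination arm more routes into the shared weekly rule.

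A second reply is that other forces act in the opposite direction. Holding capmatinib may cut peaks short, and earlier discontinuation shortens the on-treatment window and yields fewer scheduled samples. Neither is in the simulation, so the net direction in the actual data is not established.

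A third reply is that Protocol 12.5.2 itself specifies worst post-baseline grade and shift to the worst on-treatment value. The SAP follows it, and replacing those tables would demote real peaks in a trial halted for tolerability. This stands: the all-assessment tables should remain the main display.

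A reader might also infer that the adverse events of special interest, or the halt itself, are biased by this. The documents do not support that. SAP 2.8.4 builds those events from MedDRA terms on reported AEs, and the Amendment 3 rationale bases the halt on SAEs/AEs leading to interruption or discontinuation. Neither rests on the 2.8.5.2 tables.

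**Conclusion.** The concern holds in a limited form. Arm-specific repeat testing combined with a worst-of-all-samples rule can inflate the combination arm's worst-grade, shift and higher liver-threshold rows for ALT/AST, bilirubin and creatinine at equal true toxicity. For ALT >5×ULN the effect is about 1.3-1.7 times the detection per episode with no control retesting. This is roughly 0.1-1.3 of 51 subjects under assumed episode rates, and less in proportion to control retesting. The figures rest on assumed ALT courses and episode frequency and ignore any effect of capmatinib holds. Creatinine and bilirubin were not simulated; for them only the direction of the testing effect is argued.

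It would go too far to say that the combination arm will show more grade 3-4 laboratory toxicity across the board. The control retest rate is unknown, and several rows cannot move through same-analyte repeats. The tables are descriptive with no planned test, so this is a matter of interpretation and is cheap to address.

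**What to change.** In SAP 2.8.5.2:
1. Keep the all-assessment worst-grade, shift and liver-threshold tables as the main display.
2. Add a companion version for ALT/AST, bilirubin and creatinine restricted to protocol-scheduled samples (Day 1 of each cycle and EOT). This removes the difference driven by triggered repeats by construction.
3. Report the number of post-baseline tests per subject by arm.
4. Footnote the main tables to say that recommended follow-up testing differed by arm until approval of Amendment 03.

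The SAP already treats unscheduled ECGs separately when deriving baseline (2.1.1.4), so the distinction is not new to it. The cost is a few extra descriptive tables from data already collected. The scheduled-only version will miss some true peaks in both arms, which is why it should accompany the main tables and not replace them.
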